5.1.5 Planned Study Calendar

The following dates are approximate. The actual dates may differ as, for example, the study will not start until all the appropriate regulatory and ethical approvals have been obtained.

Planned subject period - FVFS (first visit, first subject) to LVLS (last visit, last subject): Q4 2018 to Q4 2023

Planned inclusion period - FVFS to FVLS (first visit, last subject): Q4 2018 to Q2 2022

Planned end of study - LVLS (last visit, last subject): Q4 2023

Planned date of final clinical study report: Q4 2024

5.2 Enrollment and Retention of Study Population

5.2.1 Recruitment Procedures

Each site will be responsible for devising a recruitment plan for enrolling eligible subjects. Advertisements and other recruitment aids will be approved by the Sponsor and the site's IRB/IEC prior to use by the clinical site.

5.2.2 Informed Consent Procedures

Informed consent is the process by which a subject's parent / legally acceptable representative voluntarily confirms his or her willingness to let his/her child participate in a particular study. Informed consent must be obtained before any study procedures are performed. The process is documented by means of a written, signed, and dated ICF.

In accordance with GCP, prior to signing and dating the consent form, the subject's parent / legally acceptable representative must be informed by appropriate study personnel about all aspects of the study that are relevant to making the decision to participate, and must have sufficient time and opportunity to ask any questions.

The actual ICF used at each center may differ, depending on local regulations and IEC / IRB requirements. However, all versions must contain the standard information found in the sample ICF provided by the Sponsor. Any change to the content of the ICF must be approved by the Sponsor and the IEC / IRB prior to the form being used.

If new information becomes available that may be relevant to the subject's parent / legally acceptable representative's willingness to continue participation in the study, this will be communicated to him / her in a timely manner. Such information will be provided via a revised ICF or an addendum to the original ICF.

ICFs will be provided in duplicate, or a photocopy of the signed consent will be made. The original will be kept by the Investigator, and the copy will be kept by the subject's parent / legally acceptable representative.

Documentation of the consent process should be recorded in the source documents.

Rationale for Including Subjects Unable to Give Consent:

MET58 is a study to be conducted in children approximately 6 weeks to 18 months of age to obtain safety and immunogenicity data (see [Section 1.4](#)).

Since these subjects are unable to give their consent, written informed consent must be obtained from the parent or legally acceptable representative in accordance with local practices before participation in the study and before any study related procedure is done (eg, collection of blood sample). The signature on the ICF must be dated by the parent / legally acceptable representative in accordance with local practices. The parent / legally acceptable representative should be able to consent for their child. The child of minor parents must not be included in the study.

5.2.3 Screening Criteria

There are no screening criteria other than the inclusion and exclusion criteria.

5.2.4 Inclusion Criteria

An individual must fulfill *all* of the following criteria to be eligible for study enrollment:

- 1) Aged ≥ 42 to ≤ 89 days on the day of the first study visit
- 2) Healthy infants as determined by medical history, physical examination and judgment of the Investigator
- 3) Informed consent form has been signed and dated by the parent(s) or other legally acceptable representative
- 4) Subject and parent/legally acceptable representative are able to attend all scheduled visits and to comply with all study procedures
- 5) Covered by health insurance according to local regulations

5.2.5 Exclusion Criteria

An individual fulfilling *any* of the following criteria is to be excluded from study enrollment:

- 1) Participation at the time of study enrollment (or in the 4 weeks preceding the first study vaccination) or planned participation during the present study period in another clinical study investigating a vaccine, drug, medical device, or medical procedure.
- 2) Receipt of any vaccine in the 4 weeks preceding the first study vaccination or planned receipt of any vaccine in the 4 weeks before and/or following any study vaccination except for influenza vaccination and rotavirus vaccination, which may be received at a gap of at least 2 weeks before or 2 weeks after any study vaccines. This exception includes monovalent pandemic influenza vaccines and multivalent influenza vaccines. This exclusion criterion does not apply to subjects in Finland, Sweden or Poland who plan to receive the licensed rotavirus vaccine concomitantly with study vaccines at study vaccination visits V1 and V2.
- 3) Receipt or planned receipt during the study period vaccination against meningococcal disease with either the study vaccine or another vaccine (ie., mono- or polyvalent, polysaccharide, or

conjugate meningococcal vaccine containing serogroups A, C, W, or Y; or meningococcal B serogroup-containing vaccine

- 4) Previous vaccination against diphtheria, tetanus, pertussis, *Haemophilus influenzae* type b (Hib), poliovirus, *Streptococcus pneumoniae*, measles, mumps, or rubella. Previous vaccination against hepatitis B specific to risk groups, as per local recommendation
- 5) Receipt of immune globulins, blood or blood-derived products since birth
- 6) Known or suspected congenital or acquired immunodeficiency; or receipt of immunosuppressive therapy, such as anti-cancer chemotherapy or radiation therapy; or long-term systemic corticosteroid therapy (prednisone or equivalent for more than 2 consecutive weeks) since birth
- 7) Family history of congenital or hereditary immunodeficiency, unless the immune competence of the potential vaccine recipient is demonstrated
- 8) Individuals with blood dyscrasias, leukemia, lymphoma of any type, or other malignant neoplasms affecting the bone marrow or lymphatic systems
- 9) Individuals with active tuberculosis
- 10) History of *Neisseria meningitidis* infection, confirmed either clinically, serologically, or microbiologically
- 11) History of diphtheria, tetanus, pertussis, poliomyelitis, hepatitis B, measles, mumps, rubella, and of *Haemophilus influenzae* type b, and / or *Streptococcus pneumoniae* infection or disease
- 12) At high risk for meningococcal infection during the study (specifically, but not limited to, subjects with persistent complement deficiency, with anatomic or functional asplenia, or subjects traveling to countries with high endemic or epidemic disease)
- 13) Individuals with underlying conditions predisposing them to invasive pneumococcal disease (specifically, but not limited to, subjects with sickle cell disease or human immunodeficiency virus [HIV] infection)
- 14) History of any neurologic disorders, including seizures and progressive neurologic disorders
- 15) History of Guillain-Barré syndrome
- 16) Known systemic hypersensitivity to any of the vaccine components, or history of a severe allergic reaction (eg., anaphylaxis) to the vaccine(s) used in the study or to a vaccine containing any of the same substances including neomycin, streptomycin, polymyxin B, glutaraldehyde, formaldehyde, and gelatin^a
- 17) Verbal report of thrombocytopenia, contraindicating intramuscular vaccination in the investigator's opinion
- 18) Bleeding disorder, or receipt of anticoagulants in the 3 weeks preceding inclusion, contraindicating intramuscular vaccination in the investigator's opinion

^a The components of all study vaccines are listed in Section 6 of the Investigator's Brochure

- 19) Chronic illness (including, but not limited to, cardiac disorders, congenital heart disease, chronic lung disease, renal disorders, auto-immune disorders, diabetes, psychomotor diseases, and known congenital or genetic diseases) that, in the opinion of the investigator, is at a stage where it might interfere with study conduct or completion
- 20) Any condition which, in the opinion of the investigator, might interfere with the evaluation of the study objectives
- 21) Moderate or severe acute illness/infection (according to investigator judgment) on the day of vaccination or febrile illness (temperature $\geq 38.0^{\circ}\text{C}$). A prospective subject should not be included in the study until the condition has resolved or the febrile event has subsided.
- 22) Receipt of oral or injectable antibiotic therapy within 72 hours prior to the first blood draw
- 23) Identified as a natural or adopted child of the Investigator or employee with direct involvement in the proposed study
- 24) Infants born preterm (by less than 37 weeks of gestation) requiring specific immunization schedule for routine childhood vaccines and/or specific care at the time of vaccination, as per national recommendations

If the subject has a primary physician who is not the Investigator, the site must contact this physician with the parent's / legally acceptable representative's consent to inform him / her of the subject's participation in the study. In addition, the site should ask this primary physician to verify exclusion criteria relating to previous therapies, such as receipt of blood products or previous vaccines.

5.2.6 Medical History

Prior to enrollment, subjects will be assessed for pre-existing conditions and illnesses, both past and ongoing. Any such conditions will be documented in the source document. Significant (clinically relevant) medical history (reported as diagnosis) including conditions/illnesses for which the subject is or has been followed by a physician or conditions/illnesses that could resume during the course of the study or lead to an SAE or to a repetitive outpatient care will be collected in the CRB. The significant medical history section of the CRB contains a core list of body systems and disorders that could be used to prompt comprehensive reporting, as well as space for the reporting of specific conditions and illnesses.

For each condition, the data collected will be limited to:

- Diagnosis (this is preferable to reporting signs and symptoms)
- Presence or absence of the condition at enrollment
- The reporting of signs and symptoms in lieu of a diagnosis is strongly discouraged.

Dates, medications, and body systems are not to be recorded, and the information collected will not be coded. Its purpose is to assist in the later interpretation of safety data collected during the study.

5.2.7 Contraindications for Subsequent Vaccinations

5.2.7.1 Temporary Contraindications

Should a subject experience one of the conditions listed below, the Investigator will postpone further vaccination until the condition is resolved. Postponement must still be within the timeframe for vaccination indicated in the Table of Study Procedures.

- 1) Febrile illness (temperature $\geq 38.0^{\circ}\text{C}$ [$\geq 100.4^{\circ}\text{F}$]) or moderate or severe acute illness / infection on the day of vaccination, according to Investigator judgment
- 2) Receipt of any vaccine (other than the study vaccine[s]) in the 4 weeks preceding any vaccination or planned receipt of any vaccine in the 4 weeks following any study vaccination except for influenza vaccination and rotavirus vaccination, which may be received at least 2 weeks before or 2 weeks after any study vaccines. This exception includes monovalent pandemic influenza vaccines and multivalent influenza vaccines. This temporary contraindication does not apply to subjects in Finland, Sweden or Poland who plan to receive the licensed rotavirus vaccine concomitantly with study vaccines at study vaccination visits V1 and V2. If, for any reason a subject receives any routine pediatric vaccine considered as study vaccine (eg, PCV10, PCV13, Hexyon®/Hexacima®) or non-study vaccine similar to the routine pediatric study vaccines (eg Infanrix hexa®, Priorix®) out of the study, the interval of at least 4 weeks following the study vaccination(s) should be respected. The investigator should make efforts to ensure that the subject receives these study vaccines within the timelines concomitantly with the investigation or control meningococcal vaccines, as per protocol corresponding visits.
- 3) Immune globulins, blood, or blood-derived products: used in the 3 months preceding any study vaccination
- 4) Immunosuppressive therapy such as anti-cancer chemotherapy or radiation therapy or long-term systemic corticosteroid therapy (prednisone or equivalent for more than 2 consecutive weeks) used in the 6 months preceding any study vaccination.

5.2.7.2 Definitive Contraindications

Should a subject experience at least 1 of the conditions listed below, the Investigator will discontinue vaccination:

- 1) Having received Meningococcal Group B vaccination since the last visit
- 2) An anaphylactic or other significant allergic reaction to the previous dose of vaccine
- 3) Any related SAE after a previous study vaccination

Subjects with a definitive contraindication will continue to be followed up for the study-defined safety and immunogenicity assessments, as applicable.

In the event of a local or national immunization program with a pandemic influenza or coronavirus vaccine or any other vaccine as needed, subjects who receive one or more doses of a pandemic influenza or coronavirus vaccine at any time during the study will not be withdrawn from the study.

The following AEs constitute absolute contraindications to subsequent vaccinations, according to their respective Summary of Product Characteristics (SmPC). If a subject should experience any of these events during the study, irrespective of causality, that subject is not to receive any additional study vaccines but should continue in the study and be followed up for safety only, as per protocol. Only the vaccine which has a related SAE or a definite contraindication will be stopped wherever it is possible to identify the vaccine that caused the event.

Meningococcal vaccines: (MenACYW conjugate vaccine or Nimenrix®):

- 1) History of Guillain-Barré syndrome within 6 weeks after vaccination with a tetanus toxoid-containing vaccine
- 2) History of an Arthus-like reaction after vaccination with a tetanus toxoid-containing vaccine
- 3) Severe allergic reaction (eg, anaphylaxis) after a previous dose of meningococcal capsular polysaccharide-, tetanus toxoid carrier protein – containing vaccines or to any component of meningococcal vaccines
- 4) Persons with familial complement deficiencies (for example, C5 or C3 deficiencies) and persons receiving treatments that inhibit terminal complement activation (for example, eculizumab) are at increased risk for invasive disease caused by *Neisseria meningitidis* groups A, C, W-135 and Y, even if they develop antibodies following vaccination with Nimenrix®.

Hexyon® or Hexacima®:

- 1) History of anaphylactic reaction after a previous administration of Hexyon® or Hexacima®
- 2) Hypersensitivity to the active substances, to any of the excipients, to trace residuals (glutaraldehyde, formaldehyde, neomycin, streptomycin, and polymyxin B), to any pertussis vaccine, or after previous administration of Hexyon® or Hexacima® or a vaccine containing the same components or constituents
- 3) Encephalopathy of unknown etiology occurring within 7 days of vaccination with a previous pertussis-containing vaccine (whole cell or acellular pertussis vaccines)
- 4) Uncontrolled neurologic disorder or uncontrolled epilepsy until a treatment regimen has been established and the condition has stabilized and the benefit clearly outweighs the risk

Prevenar 13®: (pneumococcal 13-valent conjugate vaccine; PCV13) :

- 1) Hypersensitivity to the active substances, to any of the excipients, to diphtheria toxoid, or to a previous dose of Prevenar 13®

Synflorix®: (pneumococcal polysaccharide conjugate vaccine; PCV10):

- 1) Hypersensitivity to the active substances, to any of the excipients, to any of the carrier proteins, or to a previous dose of Synflorix®

M-M-RVAXPRO® (measles, mumps, and rubella vaccine):

- 1) Hypersensitivity to any measles, mumps, or rubella vaccine, or to any of the excipients, including neomycin
- 2) Active untreated tuberculosis

- 3) Blood dyscrasias, leukemia, lymphomas of any type, or other malignant neoplasms affecting the bone marrow or lymphatic systems.
- 4) Severe humoral or cellular (primary or acquired) immunodeficiency (eg, severe combined immunodeficiency, agammaglobulinemia and acquired immune deficiency syndrome [AIDS] or symptomatic HIV infection)
- 5) Family history of congenital or hereditary immunodeficiency, unless the immune competence of the potential vaccine recipient is demonstrated.

5.2.7.3 Warnings and Precautions to Vaccination

Prior to vaccination, check the warnings and precautions for individual vaccines administered. For the licensed vaccines, refer to the individual package inserts. For MenACYW conjugate vaccine, refer to the Investigator's Brochure.

5.2.8 Contraindications for Subsequent Blood Draw

Should a subject receive oral or injectable antibiotic therapy within 3 days prior to the blood draws, the Investigator will postpone that blood draw until it has been 3 days since the subject last received oral or injectable antibiotic therapy. Postponement must still be within the timeframe for blood draw (30 to 44 days after vaccination or 30 to 51 days after vaccination, depending on the visit). If postponement would result in the sample collection falling outside of this 30 to 44 day or 30 to 51 day timeframe, the blood sample should be collected without postponement and it should be documented that the sample was taken less than 3 days after stopping antibiotic treatment.

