12.2.8.1 Per-Protocol Analysis Set for Primary Series (PPAS1)

The subjects presenting with at least one of the following relevant protocol deviations will be excluded from the PPAS1:

- Subject did not meet all protocol-specified inclusion criteria or met at least one of the protocol-specified exclusion criteria
- Subject did not complete the vaccination schedule
- Subject received a vaccine other than the one that he / she was randomized to receive
- Preparation and / or administration of vaccine was not done as per-protocol
- Subject did not receive vaccine in the proper time window
 - Visit 2: Visit 1 + 60 days (+14 days)
 - Visit 3 (Group 4 only): Visit 2 + 60 days (+14 days)
- Subject did not provide a post-dose serology sample in the proper time window or a post-dose serology sample was not drawn
 - Blood sampling 2 (BL0002):
 - Visit 3: Visit 2 + 30 days [+21 days] (Group 1, 2, 3)
 - Visit 4: Visit 3 + 30 days [+21 days] (Group 4)
- Subject received a protocol-prohibited therapy / medication / vaccine (identified among category 2 / category 3, not including the rotavirus vaccine administered at V1 and V2)
- Subject had other protocol violations that affected the subject's immune response, as determined by the clinical team before locking the database

In addition to the reasons listed above, subjects will also be excluded from the PPAS1 if their serology sample did not produce a valid test result (ie, results for all antigens are missing).

Vaccine correctness criteria apply to all the vaccines administered in the protocol, (ie, MenACYW conjugate vaccine / Nimenrix® and the concomitants vaccines).

In the event of a local or national immunization program with a pandemic influenza or coronavirus vaccine or any other vaccine as needed, subjects who receive the 1 or more doses of a pandemic influenza or coronavirus vaccine at any time during the study will not be withdrawn from the study.

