12.2.8.2 Per-Protocol Analysis Set for Booster Series (PPAS2)

The subjects presenting with at least one of the following relevant protocol deviations will be excluded from the PPAS2:

- Subject did not meet all protocol-specified inclusion criteria or met at least one of the protocol-specified exclusion criteria
- Subject did not complete the vaccination schedule
- Subject received a vaccine other than the one that he / she was randomized to receive

- Preparation and / or administration of vaccine was not done as per-protocol
- Subject did not receive vaccine in the proper time window for the booster dose at 12 to 18 months of age (all groups) or at least 180 days after Visit 3 (Group 4)
- Subject did not provide a post-dose serology sample in the proper time window or a post-dose serology sample was not drawn
 - Blood sampling 4 (BL0004):
 - Visit 5: Visit 4 + 30 days [+21 days] (Group 1, 2, 3)
 - Visit 6: Visit 5 + 30 days [+21 days] (Group 4)
- Subject received a protocol-prohibited therapy / medication / vaccine (identified among category 2 / category 3)
- Subject had other protocol violations that affected the subject's immune response, as determined by the clinical team before locking the database

In addition to the reasons listed above, subjects will also be excluded from the PPAS2 if their serology sample did not produce a valid test result (ie, results for all antigens are missing).

Vaccine correctness criteria apply to all the vaccines administered in the protocol, ie, MenACYW conjugate vaccine / Nimenrix® and the concomitants vaccines. A licensed Measles, Mumps and Rubella vaccine must be received either during the study visit (Visit 4/Visit 5) or with a gap of at least 4 weeks before any study vaccines or after the end of the study. In the event of a local or national immunization program with a pandemic influenza or coronavirus vaccine or any other vaccine as needed, subjects who receive the 1 or more doses of a pandemic influenza or coronavirus vaccine at any time during the study will not be withdrawn from the study.

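### Protocol 5.2.8 limits antibiotic postponement by a 30 to 44 day draw window that no blood draw has; every post-dose draw is 30 to 51 days

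*Protocol*

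**What the plan says.** Protocol 5.2.8 requires a draw to be put off until 3 days after the last oral or injectable antibiotic, provided it stays inside the draw window, which it gives as "30 to 44 days after vaccination or 30 to 51 days after vaccination, depending on the visit". It then says what to do when waiting would overrun. For a sample "falling outside of this 30 to 44 day or 30 to 51 day timeframe, the blood sample should be collected without postponement", and the site documents that fewer than 3 days had passed.

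The per-protocol definitions give one window for all post-dose draws:

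- Protocol 12.2.8.1 (PPAS1), BL0002: "Visit 3: Visit 2 + 30 days [+21 days] (Group 1, 2, 3") and "Visit 4: Visit 3 + 30 days [+21 days] (Group 4").
- Protocol 12.2.8.2 (PPAS2), BL0004: "Visit 5: Visit 4 + 30 days [+21 days] (Group 1, 2, 3") and "Visit 6: Visit 5 + 30 days [+21 days] (Group 4").

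SAP 5.2.2.1 and 5.2.2.2 repeat these windows. The two Tables of Study Procedures and Protocol 5.1.3, 5.1.4 and 7 also give 30 (+21) days. The antibiotic footnote to the procedures tables states the same postponement rule, but refers only to the draw window and gives no day numbers.

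Protocol 6.7 classes systemic antibiotics in the 72 hours before a draw for meningococcal testing as Category 3. Category 3 is an exclusion from both PPAS1 and PPAS2.

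**The concern.** The cut-off in 5.2.8 is an instruction. It decides whether a site waits for a clean sample or draws at once. The section offers two limits and leaves the choice to the visit, but never says which visit has the shorter one, and no visit does.

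A site that picked 44 days would draw under antibiotics when the protocol's own evaluability window still allowed a clean draw. The child would then drop out of the per-protocol set for that series. PPAS2 carries the primary objective and PPAS1 carries secondary objective 1 (Protocol 12.2.9), so the cost would be evaluable subjects lost for no reason.

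**Working it through.** **1. Every draw and its window**

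| Draw | Groups | Visit | Window |
|---|---|---|---|
| BL0001 | all | 1 | before first vaccination; no post-dose window |
| BL0002 | 1, 2, 3 | 3 | 30 to 30 + 21 = 51 days after Visit 2 |
| BL0002 | 4 | 4 | 30 to 51 days after Visit 3 |
| BL0003 | all | 4 (Group 4: 5) | before toddler dose; no post-dose window |
| BL0004 | 1, 2, 3 | 5 | 30 to 51 days after Visit 4 |
| BL0004 | 4 | 6 | 30 to 51 days after Visit 5 |

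All four post-dose draws have 30 to 51 days and none has 30 to 44. A limit of 44 needs 30 + 14. The only +14 day windows for visits are "Visit 2: Visit 1 + 60 days (+14 days") and "Visit 3 (Group 4 only): Visit 2 + 60 days (+14 days"). These are vaccination visits at 60 to 74 days with no blood draw.

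**2. Visit days on which the two limits disagree**

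Let d be the visit day. The longest wait after a finished course is 3 days, so clearance falls on day d + 3.

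- A 44-day limit forces a draw when d + 3 > 44, so d ≥ 42.
- A 51-day limit still allows the wait when d + 3 ≤ 51, so d ≤ 48.
- A site that treats day 44 as the end of the window has d ≤ 44.

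Together these give d = 42, 43 and 44, with clearance on days 45, 46 and 47. The window from day 30 to day 51 has 22 days, so the share is 3/22 = 14%.

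If k days of treatment remain, clearance falls on d + k + 3. The conflict band then moves earlier and can be wider: k = 7 gives days 35 to 41. The documents give no course lengths, so this is not counted below.

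**3. Children affected**

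The documents do not say how many children are on antibiotics at a planned draw. Assume 2 to 5%, visits spread evenly over the 22 days, and every site using 44 days.

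- 716 × 0.02 × 3/22 = 2.0
- 716 × 0.05 × 3/22 = 4.9

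That is about 2 to 5 per arm per draw. Two variations:

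- On the 528 expected to be evaluable: 528 × 0.02 × 3/22 = 1.4 to 528 × 0.05 × 3/22 = 3.6.
- If such sites booked all visits on days 30 to 44 (15 days): 716 × 0.02 × 3/15 = 2.9 to 716 × 0.05 × 3/15 = 7.2.

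At sites that follow the visit tables the number is zero.

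**4. Effect on primary power**

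Inputs from Protocol 12.5: 528 evaluable per group, margin 1.5, one-sided 2.5%, log10 SDs of 0.7 (A, C), 0.5 (Y) and 0.6 (W). Power per serogroup is Φ(log10(1.5) / (SD × √(2/n)) − 1.96). At n = 528 this gives 98.3% for A and C, above 99.9% for Y and 99.75% for W. The product is 96.4%, against 96.2% in the plan. The plan's rounded figures multiply to its total: 0.983 × 0.983 × 0.999 × 0.997 = 96.2%.

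An extra PPAS loss of 4.9/716 = 0.7% lies between the first two rows:

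| Extra loss | n per group | Overall power |
|---|---|---|
| 0.5% | 524 | 96.3% |
| 1% | 521 | 96.2% |
| 2% | 514 | 95.9% |

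**The case against.** The strongest reply is that the applicable limit is already on the page. The sentence that names 44 days also names 51 and sends the site to the visit. Every visit instruction and both procedures tables then give +21 days for post-dose draws. Nothing in the documents shows that any site used 44. This stands, and it is why the expected loss is small and may be zero.

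It also stands that the rule is identical in Groups 1 and 2, where the meningococcal vaccine is given in a modified double-blind manner (Protocol 6.4). No mechanism for between-arm bias is visible.

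It does not follow that this is only proofreading. Section 5.2.8 is the one place where the postponement rule carries day numbers. It gives the wrong one twice and does not say where it applies. The SAP does not settle the matter.

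Two stronger readings are tempting:

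- A reader might infer that, for a 3-day wait, visits on all of days 42 to 48 are at stake. A site that regards day 44 as the end of the window would already count days 45 to 48 as out of window. A site that draws on those days is evidently working to 51.
- A reader might blame the 44-day text for antibiotic-affected titres in the FAS. That would hold for any sample drawn under antibiotics, including one properly drawn near day 51, so this text is not its cause.

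**Conclusion.** The 30 to 44 day limit is wrong as written. It contradicts the Tables of Study Procedures and both PPAS definitions, and it sits in a rule that decides whether a sample is taken under antibiotics.

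The consequence is conditional and minor: about 2 to 5 avoidable Category 3 exclusions per arm per draw, and none where sites follow the visit tables. That range rests on an assumed 2 to 5% antibiotic use, an even spread of visits, a wait of 3 days and every site applying 44. The contradiction itself needs no assumption.

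A reader might infer a threat to the sample size. The figures do not support that: an extra loss of 1% leaves about the stated 96.2%, and 2%, well above anything counted here, leaves 95.9%.

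**What to change.** Reconcile Protocol 5.2.8 with the Tables of Study Procedures and the PPAS windows by removing both mentions of the 30 to 44 day limit. The postponement limit for post-dose draws then matches the 30 to 51 days used for evaluability. Tell sites of the correction. The cost is a wording change and a short note; no endpoint, analysis set or sample size changes.

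If sampling is already complete, list the post-dose draws taken within 72 hours of a systemic antibiotic for which clearance would have fallen by day 51, and report how many PPAS exclusions were avoidable. SAP 5.7 says the medication category fields were inactivated and medications coded by dictionary instead, so the listing would have to start from the coded drug and its dates.
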